8.2.4.3. Electrocardiograms

12-lead ECG with categorical results (Normal, Abnormal [Not clinically significant], Abnormal [clinically significant]) will be summarized. Shift tables showing results from baseline to worst post baseline will be provided. A patient listing will also be provided.

8.2.4.4. Vital Signs

For systolic blood pressure, diastolic blood pressure, pulse, and respiration summary statistics for baseline values and maximum change (maximum increase, maximum decrease and no change) from baseline will be summarized based on the safety analysis set.

Summaries of markedly abnormal vital signs parameters, including blood pressure (BP), pulse, and BMI, will be presented.

Values for vital signs for all patients will be presented in a listing, and patients with markedly abnormal values will be flagged.

Markedly abnormal ranges for vital signs parameters are given in the following table.

Vital Sign Parameter	Markedly Abnormal (Low)	Markedly Abnormal (High)
Systolic BP	Absolute value ≤ 90 mmHg, or a decrease from baseline ≥20 mmHg	Absolute value ≥ 180 mmHg, or an increase from baseline ≥20 mmHg
Diastolic BP	Absolute value ≤ 50 mmHg, or a decrease from baseline ≥15 mmHg	Absolute value ≥ 105 mmHg, or an increase from baseline ≥ 15 mmHg
Pulse	Absolute value ≤ 50 bpm	Absolute value ≥ 120 bpm
BMI	Absolute value ≤ 18 kg/m ²	Absolute value ≥ 25 kg/m ²

Table Vital Sign Threshold of Interest

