# 1.3 GLP Toxicology

GLP 28-day repeat dose toxicology studies were performed in both rats and dogs at doses of 10, 30 and 100 mg/kg/day by oral gavage.

In the rat study, 100 mg/kg was not tolerated by the male rats. Toxic observations include significant weight loss, soft feces and diarrhea, and decreased food consumption, which led to early sacrifice. These observations recovered in the remaining male rats within 14 days after termination of dosing. Female rats receiving 100 mg/kg/day showed weight loss during the first week of dosing, however weight gain recovered during the continued dosing phase without significant abnormal clinical observations.

In the rat study, abnormal laboratory findings (azotemia, hyponatremia, hypochloremia, hyperkalemia, polycythemia, neutrophilia, monocytosis, and lymphopenia) were observed primarily in moribund male rats dosed at 100 mg/kg. These findings are consistent with acute renal failure in the setting of dehydration and diarrhea. In rats dosed at 100 mg/kg for 28 days, there was mild decrease in sodium, chloride and albumin levels and mild elevation of white blood cells, red blood cells, neutrophils, lymphocytes and monocytes. No significant abnormal laboratory findings in recovery rats, suggesting these abnormal laboratory findings are reversible. There were no abnormal laboratory findings in rats dosed at 10 and 30 mg/kg.

In the rat study, histopathological findings were noted in the rats dosed at 100 mg/kg, primarily in mordibund male rats, including microscopic changes in the stomach and urinary bladder (focal or multifocal chronic ulceration, epithelial hyperplasia, chronic active inflammation or hemorrhagic changes), in lymphoid tissues (mild to marked lymphoid atrophy with mild to moderate lymphocyte apoptosis in thymus; mild to moderate lymphoid atrophy and mild to moderate mastocytosis in mesenteric lymph nodes; mild to moderate lymphoid atrophy in 2 moribund male rats of the 100 mg/kg group and some elevation of hemosiderosis in the spleen) and in adrenal glands (mild cortical vacuolation). These findings are considered non-specific changes related to the test vehicle in the setting of dehydration and diarrhea. There were no significant histopathological findings in recovery rats, suggesting these histopathological changes are reversible. There was no significant test vehicle related microscopic changes in rats dosed at 30 mg/kg and 10 mg/kg.

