In the rat study, toxicokinetics showed that all dose groups in rats achieved BBI608 exposure well above the predicted exposure levels needed for efficacy with exposure lasting beyond 10 hours.

For the dog study, toxicity was observed in dogs receiving 100 mg/kg/day consisting of mild weight loss, as well as clinical observations including emesis, diarrhea, mucoid and soft feces. These adverse effects were reversible within 14 days in the setting of continued dosing. No treatment related clinical pathology, gross pathology or histopathological effects were observed at any dose level. All dose groups achieved plasma levels of BBI608 above the predicted levels needed for efficacy, with exposure lasting beyond 10 hours.

The no observable adverse effect level (NOAEL, based on clinical observation, laboratory tests, gross and histopathological changes) for rats administered BBI608 daily orally over 28 days was 30 mg/kg/day (human equivalent dose: 180 mg/m²) and the NOAEL in dogs administered BBI608 daily orally over 28 days was 30 mg/kg/day (human equivalent dose: 600 mg/m²).

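### The SAP flags BMI by absolute value only and summarises no weight change, so a patient unflagged at entry can lose up to just under 28% of body weight without a vital-sign flag

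*SAP*

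**What the plan says.** SAP section 8.2.4.4 (Vital Signs) plans three outputs.

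- **Change summary.** It is planned "For systolic blood pressure, diastolic blood pressure, pulse, and respiration summary statistics for baseline values and maximum change" from baseline. Weight and BMI are not named.
- **Threshold summary.** "Summaries of markedly abnormal vital signs parameters, including blood pressure (BP), pulse, and BMI, will be presented". The limits stand in the table that follows. For systolic pressure the low limit is "Absolute value ≤ 90 mmHg, or a decrease from baseline ≥20 mmHg", and diastolic pressure has a matching change limb of 15 mmHg. For BMI the low limit is "Absolute value ≤ 18 kg/m" squared and the high limit is "Absolute value ≥ 25 kg/m" squared, with no change limb on either side. Weight has no row.
- **Listing.** "Values for vital signs for all patients will be presented in a listing, and patients with markedly abnormal values will be flagged".

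Elsewhere the SAP uses weight as a baseline demographic and in dose calculation (section 8.2.1). It plans no summary of weight change.

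The protocol collects weight at baseline (section 5.2), at the cycle 1 assessment visits (sections 5.3.1 to 5.3.3), once per cycle from cycle 2 (section 5.3.3.6) and at end of study (section 5.5).

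On animal toxicity, protocol section 1.3 says of rats at 100 mg/kg: "Toxic observations include significant weight loss, soft feces and diarrhea, and decreased food consumption, which led to early sacrifice". For dogs at 100 mg/kg/day it describes toxicity "consisting of mild weight loss, as well as clinical observations including emesis, diarrhea, mucoid and soft feces".

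**The concern.** A safety flag should respond to what happens on treatment. An absolute BMI limit of 25 responds mainly to how heavy the patient was at enrolment. A patient who enters above it carries the flag for reasons unrelated to treatment and can lose it by losing weight, so deterioration reads as a return to normal. At the other end, a limit of 18 is far from most of the unflagged range of 18 to 25, so a large loss may never reach it.

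BMI is the only parameter in the threshold table with neither form of change reporting. Both blood pressures have change limbs and also appear in the change summary. Pulse has no change limb but does appear in the change summary.

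Safety is part of the primary objective (protocol section 2.1), and diarrhea and nausea were the most common events in Phase I (protocol section 1.4). Weight is a simple objective measure in that setting. As the plan stands, no planned summary uses its change.

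**Working it through.** The documents state no weight-loss figure, so there is none to reproduce. The inputs are the two BMI limits in SAP section 8.2.4.4. Height is taken as fixed, so percent change in BMI equals percent change in weight.

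Let B be BMI at entry.

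- Loss at which the low flag fires: (B − 18) / B.
- Loss beyond which the high flag clears, for B of 25 or more: (B − 25) / B.

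| BMI at entry | Status at entry | Loss that reaches the low flag | Loss beyond which the high flag clears |
|---|---|---|---|
| 19 | unflagged | 1/19 = 5.3% | – |
| 20 | unflagged | 2/20 = 10.0% | – |
| 22 | unflagged | 4/22 = 18.2% | – |
| 24 | unflagged | 6/24 = 25.0% | – |
| 24.9 | unflagged | 6.9/24.9 = 27.7% | – |
| 30 | flagged high | 12/30 = 40.0% | 5/30 = 16.7% |
| 35 | flagged high | 17/35 = 48.6% | 10/35 = 28.6% |

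**Upper limit for patients unflagged at entry.** These patients have B above 18 and below 25. As B approaches 25, the loss needed approaches (25 − 18)/25 = 28.0% from below. A patient at exactly 25 is already flagged high, so 28% is a limit that is never quite reached. At an assumed height of 1.70 m, BMI 25 is 25 × 2.89 = 72.25 kg and BMI 18 is 18 × 2.89 = 52.02 kg, a difference of about 20 kg.

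**Who can lose a given fraction with no flag at any time.** The entry BMI must exceed 18/(1 − loss) and be below 25. For a 10% loss this is 18/0.90 = 20.0 to 25. For a 20% loss it is 18/0.80 = 22.5 to 25.

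**Direction of the high flag.** A patient entering at BMI 30 is flagged at first, becomes unflagged after losing more than 16.7%, and stays unflagged until the loss reaches 40.0%. Over that range the flag moves opposite to the patient's condition.

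**The case against.** The strongest reply is that weight loss has other routes into the report. An investigator can record it as an adverse event, which is then graded by CTCAE 4.0 and tabulated by preferred term and maximum grade (SAP section 8.2.4.1). Individual weights should also appear in the vital-signs listing, since the protocol classes weight as a vital sign. This stands. A reader might infer that weight loss would go unseen, and the documents do not support that. What is missing is an objective summary that does not depend on the investigator recognising and reporting the event. For laboratory data the SAP does not rely on adverse event reports alone: section 8.2.4.2 adds change-from-baseline summaries and shift tables.

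The animal findings should not be over-read either. Diarrhea and soft feces were also seen in both species. The dog weight loss was mild and reversed within 14 days while dosing continued, and female rats regained weight on continued dosing. Weight loss is one toxicity among several, seen at the top dose.

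It is also fair that tolerability of the two starting doses is to be judged by adverse event profile and achieved dose intensity (protocol section 2.2), with diarrhea days and compliance (protocol section 10.8). Weight was never a chosen tolerability measure. The sub-cohorts begin with six patients each, are allocated sequentially and are exploratory. The study is non-randomised and every arm receives BBI608, so a weight table could not separate drug effect from advanced cancer.

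Finally, the threshold summary is worded as non-exhaustive, and SAP section 8.1 allows additional exploratory analyses. A weight table could therefore be added later, but that does not repair the BMI limits as written.

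**Conclusion.** The point holds as a reporting weakness in a supporting safety table. Followed as written, the BMI rule lets a patient unflagged at entry lose up to just under 28% of body weight with no vital-sign flag, and it can remove a flag because a patient has lost weight.

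The size needs care. A reader might take 28% as typical. It is the upper limit for patients unflagged at entry, and the loss needed falls to 10.0% at BMI 20 and 5.3% at BMI 19. A reader might also infer that baseline overweight will dominate the table. The documents give no BMI distribution, and section 8.2.4.4 does not say whether the summary counts baseline values or only post-baseline ones, so the share of patients affected cannot be computed.

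The arithmetic rests only on the two stated limits and on fixed height. No decision rule and no analysis of disease control rate is touched. The priority is low, but the remedy is nearly free.

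**What to change.** In SAP section 8.2.4.4:

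1. Replace the BMI row of the threshold table with a change-from-baseline criterion for weight or BMI.
2. Add a descriptive table of maximum percent weight loss from baseline by arm and sub-cohort, with counts at cut-offs stated in advance. Losses of 5%, 10% and 20% would serve as an example. They do not appear in the documents and should be checked against the CTCAE 4.0 grading that the SAP already uses.

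A percent criterion treats all entry sizes alike. At 10%, a patient entering at BMI 24.9 would be counted at 24.9 × 0.90 = 22.4 instead of at 18, and one entering at BMI 30 would be counted at 30 × 0.90 = 27.0 instead of going from flagged to unflagged below 25.

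The cost is one replaced row and one extra table from data already collected. The table should be labelled as supportive, since without a control arm it cannot attribute weight loss to the drug.

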10. APPENDICES

Appendix 1.1. Response Criteria

	Evaluation of target lesions	
Complete Response (CR):	Disappearance of all target lesions	
	Any pathological lymph nodes must have reduction in short axis of <10mm	
Partial Response (PR):	At least a 30% decrease in the sum of the LD of target	
	lesions, taking as reference the baseline sum LD	
Progressive Disease (PD):	At least a 20% increase in the sum of the LD of target	
	lesions, taking as reference the smallest sum LD recorded	
	since the treatment started. In addition to the increase of	
	20%, the sum must also demonstrate an absolute increase of	
	at least 5mm. The appearance of one or more new lesions is	
	also considered progression.	
Stable Disease (SD):	Neither sufficient shrinkage to qualify for PR nor sufficient	
	increase to qualify for PD, taking as reference the smallest	
	sum LD since the treatment started	

	Evaluation of non-target lesions	
Complete Response (CR):	Disappearance of all non-target lesions and normalization of	
	tumor marker level. All lymph nodes must be non-	
	pathological in size (<10mm short axis)	
Stable Disease (SD):	Persistence of one or more non-target lesion(s) and/or	
	maintenance of tumor marker level above normal limits	
Progressive Disease (PD):	Appearance of one or more new lesions and/or unequivocal	
	progression of existing non-target lesions	

Patients with an imaging assessment that meets criteria for either complete response (CR) or partial response (PR) must have a repeat radiologic assessment approximately 4 weeks after the assessment in which CR or PR criteria were met.

Target lesions	Non-Target lesions	Evaluation of New lesions	Overall response
CR	CR	No	CR
CR	Non-CR/non-PD	No	PR
CR	Not evaluated	No	PR
PR	Non-PD or not all evaluated	No	PR
SD	Non-PD or not all evaluated	No	SD
PD	Any	Yes or No	PD
Any	PD	Yes or No	PD
Any	Any	Yes	PD

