### **5.4** Tumor Evaluation Visits

Disease status and tumor response will be assessed in eight-week intervals up to one year after starting therapy (calculated from the first dose of BBI608) or as clinically indicated. Standard

imaging studies should be performed according to institutional procedures. Tumor response for solid tumors will be evaluated using the guidelines for Response Evaluation Criteria in Solid Tumors (RECIST 1.1) outlined in Section 9.

Once progression of disease during therapy is documented, patients must be taken off treatment and may receive any therapy as determined by their treating physician.

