3.2. Secondary Endpoints

- PK parameters of napabucasin administered in combination with cetuximab, or panitumumab, or capecitabine.
- PK parameters of capecitabine and metabolite (5-FU).
- Pharmacodynamics parameters (or biomarkers) of napabucasin administered in combination with cetuximab, or panitumumab, or capecitabine. Response (increase or decrease) of several biomarkers of napabucasin from biopsied tumors following napabucasin administration will be examined in patients with accessible tumors who consent to an optional biopsy.
- Objective Response Rate (ORR)

ORR is defined as the percentage of patients with a best overall response (BOR) of complete response (CR) or partial response (PR). The categorizations of response (CR, PR, SD, PD, and NE) and the derivations of BOR is provided in Appendix 1.1 and 1.2.

• Progression Free Survival (PFS) and Overall Survival (OS)

PFS is defined as the time from the date of first treatment (or date of enrollment in sensitivity analysis) to the date of first documentation of progressive disease (PD) or death due to any cause, whichever occurs first.

OS is defined as the time from the date of treatment (or date of enrollment in sensitivity analysis) to the date of death. Patients without documentation of death at the time of analysis will be censored at the date last known to be alive.

• Dose Limiting Toxicities (DLTs): For definition of DLT, see Section 4.5 of the protocol amendment 2 [5].

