8.2.2. Analysis for Primary Endpoint

The primary endpoint is DCR, which is defined as the proportion of patients with a documented complete response (CR), partial response (PR), and stable disease (SD). The categorization of response (CR, PR, SD, PD, and NE) and the derivations of BOR are provided in Appendix 1.1.

DCR will be summarized by arm and sub-cohort for the response evaluable set. DCR point estimates will be provided along with the corresponding 2-sided 95% confidence intervals using an exact method [1]. Sensitivity analysis of DCR will be performed for all patients in the safety set.

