Appendix 1.2. Evaluation of Best Overall Response

The best overall response (BOR) is the best response recorded from start date until disease progression or start of new anti-cancer therapy. BOR is determined by the following order.

CR: One objective status of CR documented before progression and start of new anti-cancer therapy.

PR: One objective status of PR documented before progression and start of new anti-cancer therapy, but not qualifying as CR.

SD: At least one objective status of SD documented at least (8 weeks -1 days) after start date and before progression and the start of new anti-cancer therapy but not qualifying as CR or PR.

PD: Progression documented within (16 weeks + 1 days) after start date and not qualifying as uCR, uPR, or SD.

NE: All other cases. Note that reasons for NE should be summarized and the following reasons could be used:

- Early death (*Note: death prior to (8 weeks 1 days) after start date*)
- No post-baseline assessments
- All post-baseline assessments have overall response of NE
- New anti-cancer therapy started before first post-baseline assessment
- SD too early (< (8 weeks 1 days) after start date)
- PD too late (> (16 weeks + 1 days) after start date)

Special and rare cases where BOR is NE due to both early SD and late PD will be classified as 'SD too early'.

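### The SAP requires a repeat scan after every CR or PR but gives it no confirmatory role, so ORR is a single-assessment (unconfirmed) rate that is not labelled as such

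*SAP*

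**What the plan says.** **Repeat scan.** Below the lesion criteria, SAP Appendix 1.1 says that patients who meet CR or PR criteria "must have a repeat radiologic assessment approximately 4 weeks after the assessment in which CR or PR criteria were met". It does not state the purpose of the scan.

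**Best overall response.** Appendix 1.2 asks for one assessment only: "CR: One objective status of CR documented before progression and start of new anti-cancer therapy", and "PR: One objective status of PR documented before progression and start of new anti-cancer therapy, but not qualifying as CR". Its PD line excludes patients by the words "not qualifying as uCR, uPR, or SD". Neither uCR nor uPR is defined or derived anywhere in the SAP.

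**ORR.** SAP section 3.2 lists ORR as a secondary endpoint, the percentage of patients whose best overall response is CR or PR, and refers to Appendices 1.1 and 1.2. It does not say confirmed or unconfirmed. SAP section 8.2.3.3 reports it by arm and sub-cohort.

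**DCR.** SAP section 8.2.2 pools the three categories: "The primary endpoint is DCR, which is defined as the proportion of patients with a documented complete response (CR), partial response (PR), and stable disease". For the derivation of best overall response it points to Appendix 1.1, although the derivation stands in Appendix 1.2.

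**Protocol.** Section 9.4 takes the best response recorded and has no confirmation rule. Section 5.4 sets the scan interval: "Disease status and tumor response will be assessed in eight-week intervals up to one year after starting therapy", or as clinically indicated. Appendix A places imaging before cycle 3 and every other cycle after that. Neither place has a 4-week repeat scan after a response.

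**The concern.** A compulsory repeat scan about 4 weeks after a response would ordinarily serve to confirm that response. The rule that produces the reported result never uses it that way, and the stray uCR/uPR labels suggest a confirmed/unconfirmed scheme that was only partly carried over. Three things follow.

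- A reader of the study report who knows that repeat scans were required could take the ORR to be confirmed.
- A programmer who follows the cross-reference in SAP section 8.2.2 to Appendix 1.1 could reasonably build in confirmation, while one who follows Appendix 1.2 would not. The two could report different ORRs from the same data.
- The trial is open label (protocol section 7.4), imaging follows institutional procedures (protocol section 5.4), and no central reading is described. A rule that takes the best single scan is then open to measurement error near the 30% shrinkage cut-off.

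The sub-cohorts are small. With the 6 patients first assigned to each, one response more or less moves ORR by 1/6, about 17 percentage points.

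**Working it through.** The documents give no assumed ORR, no confirmation rate, and no sample size or power based on ORR. There is no planned figure to reproduce, so the check is first logical and then illustrative.

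**1. The rules side by side**

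| Place | What it requires for CR or PR |
|---|---|
| SAP Appendix 1.1 | Repeat imaging about 4 weeks later; purpose not stated |
| SAP Appendix 1.2, CR and PR lines | One assessment |
| SAP Appendix 1.2, PD line | Uses uCR and uPR, undefined |
| SAP section 3.2 | ORR from best overall response, no qualifier |
| Protocol section 9.4 | Best recorded response, no confirmation |
| Protocol section 5.4 and Appendix A | Scans about every 8 weeks; no 4-week repeat |

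The operative SAP rule and the protocol agree on a single assessment. What does not fit is the repeat scan without a stated use, the undefined labels and the unlabelled endpoint.

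**2. Direction**

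Every patient with a confirmed response has at least one CR or PR assessment. Confirmed responders are therefore a subset of single-assessment responders, and in the same patients

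ORR (single assessment) ≥ ORR (confirmed).

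**3. Size, for illustration**

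Inputs: n = 50 per arm (SAP section 4.3, approximate upper figure); exact two-sided 95% intervals (SAP section 8.1.2). The single-assessment ORR (10%, 20%, 30%) and the share confirmed (100%, 80%, 60%) are assumptions. Confirmed responders = n × ORR × share confirmed.

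| Assumed ORR (all confirmed) | 80% confirmed | 60% confirmed |
|---|---|---|
| 5/50 = 10% (3.3 to 21.8) | 4/50 = 8% (2.2 to 19.2) | 3/50 = 6% (1.3 to 16.5) |
| 10/50 = 20% (10.0 to 33.7) | 8/50 = 16% (7.2 to 29.1) | 6/50 = 12% (4.5 to 24.3) |
| 15/50 = 30% (17.9 to 44.6) | 12/50 = 24% (13.1 to 38.2) | 9/50 = 18% (8.6 to 31.4) |

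The gap runs from 0 (all confirmed) to 30 − 18 = 12 percentage points.

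**4. One borderline patient, for illustration**

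Assume a true shrinkage of 20% and a normal measurement error with SD 10 points. The chance that one scan crosses the PR cut-off is p = Φ((−30 + 20)/10) = Φ(−1) = 0.159. With two scans and independent errors:

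- at least one PR: 1 − (1 − 0.159)² = 0.29
- both PR: 0.159² = 0.025

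With SD 7, p = 0.077 and the figures are 15% and 0.6%. Both percentage changes share one baseline sum, so their errors are likely to be positively correlated. At an assumed correlation of 0.5 the pairs become 25% and 6.3% (SD 10), and 13% and 2.2% (SD 7). With independent errors, SD 10 and a true shrinkage of 10%, the chance of at least one PR falls to 4.5%; with no shrinkage it is 0.3%. These figures show how the mechanism works near the cut-off. They are not an estimate of ORR in this trial.

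**5. Effect on DCR**

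DCR counts CR, PR and SD alike. If confirmation were required, a PR reclassified as SD would still count, provided that the timing rule is met: "SD: At least one objective status of SD documented at least (8 weeks -1 days) after start date". Only a responder scanned earlier than that, with no later qualifying scan, could drop to NE.

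**The case against.** A reader might infer that ORR is biased upward. Bias needs a target, and neither document names a confirmed ORR as the target. The SAP defines ORR by a single-assessment best response, states that rule openly, and agrees with protocol section 9.4. What can be said is that this ORR is at least as high as a confirmed one.

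A reader might also infer that the repeat scan is ignored or has no role in any analysis. The SAP does not support that. The scan is a tumour assessment: it can raise PR to CR, show progression, or move the last adequate assessment for PFS (Appendices 1.2 and 1.3). It also feeds the listings of first and last CR/PR dates and the swimmer and spider plots in SAP section 8.2.3.3, where an unsustained response would show. Only a confirmatory use is missing. Appendix 1.1 does not speak of confirmation or make the repeat scan a condition for CR or PR, so confirmation is the natural reading of its purpose, not the stated one.

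Two further points stand.

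- The protocol does not schedule the 4-week scan, so these data may be sparse. A confirmation rule that counted every missing later scan as non-response would push ORR down for reasons unrelated to response.
- The consequence is limited. SAP section 4.1 has no hypothesis testing, protocol section 10.3 treats anti-tumour activity as exploratory, and protocol section 2.1 names PFS and OS, not ORR, as secondary endpoints.

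One can argue that a second ORR is then a matter of preference. The labelling, the undefined terms and the cross-reference need correction in any case. A confirmed figure beside the planned one costs little and shows how far the result depends on single scans.

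**Conclusion.** The point holds as one of specification and labelling. The SAP asks for a repeat scan, gives it no confirmatory role, leaves uCR and uPR undefined, and reports an ORR that is unconfirmed without the label. That ORR cannot be lower than a confirmed ORR; this follows from the definitions and needs no assumption. The documents do not determine the gap. The range of 0 to 12 percentage points rests on 50 patients per arm, an assumed single-assessment ORR of 10% to 30%, and an assumed 60% to 100% of responses confirmed. DCR is almost unaffected and no decision depends on ORR, so this is a low-cost improvement and no threat to the trial's main result.

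**What to change.** 1. Keep the single-assessment ORR, which agrees with protocol section 9.4, and label it unconfirmed in SAP sections 3.2 and 8.2.3.3 and in the tables.
2. In Appendix 1.2, derive a confirmed response as well: CR or PR seen again at least 4 weeks later, on the repeat scan or the next scheduled scan. Report the confirmed ORR beside the unconfirmed one.
3. Show responders with no later adequate scan as a separate count, so that missing scans are not silently treated as non-response.
4. Define uCR and uPR as the unconfirmed categories, or replace them with CR and PR in the PD line.
5. In SAP section 8.2.2, point to Appendix 1.2 for the derivation of best overall response. Leave DCR on the present single-assessment rule.
6. Reconcile the 4-week repeat scan in SAP Appendix 1.1 with the 8-week imaging schedule in protocol section 5.4 and Appendix A, and state the purpose of the repeat scan.

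The cost is one extra derivation, one table row with the count, and some text edits. The analysis needs no scans beyond those that the SAP requires or the protocol schedules. The downside is a confirmed ORR that is equal to or lower than the planned figure, and that may be hard to interpret if many responders have no later scan, which is why the separate count is needed.
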